5 TRIAL POPULATION

5.1 Screening population

All infants born at 33 0/7 to 35 6/7 weeks gestation and ≥ 1500 grams are screened for study entry if they are admitted to the NICU with an admitting diagnosis of acute perinatal asphyxia, neonatal depression, encephalopathy and/or fetal acidemia at less than 6 hours of age. All these infants at < 6 hours of age are evaluated by clinical and biochemical criteria and further assessed by neurological examination. Both inborn and outborn infants are evaluated. From this population, babies are screened for inclusion in the trial using the following eligibility criteria.

Eligibility

Inclusion criteria

Infants 33 0/7 to 35 6/7 weeks GA (best obstetrical estimate) and ≥ 1500 grams birth weight (to minimize potential difficulties placing esophageal probe) who meet clinical, biochemical and neurologic criteria for moderate to severe NE in this GA range at ≤ 6 hours age:

1) Biochemical:

Cord gas or if unavailable, blood gas within first hour of life with $\text{pH} \leq 7.00$ or base deficit (BD) ≥ 16 mEq/L, OR

2) Clinical in the absence of blood gas results or Clinical with more modest fetal acidemia (cord or 1st hour of life blood gas with a pH of 7.01-7.15 or BD > 10.0 to 15.9mEq/L):

a) Acute perinatal event (e.g., abruptio placenta, cord prolapse, uterine rupture, maternal cardiac or respiratory arrest, severe FHR abnormality such as variable or late decelerations,) AND

b) Requirement for positive pressure ventilation for apnea OR poor respiratory effort since birth for at least 10 minutes OR 10-minute Apgar score ≤ 5

AND

3) Neurologic:

Clinical Seizures OR modified Sarnat score with moderate or severe abnormalities in at least 3 of the 6 categories; at least one must be altered level of consciousness (lethargy or stupor/coma) as determined by a certified examiner.

All infants who meet criteria for potential inclusion should undergo standard neurologic exam as for infants ≥ 36 wks GA being considered for hypothermia, with findings recorded.

Criteria for exclusion in hypothermia trial

1) Receipt of paralytic agent or sufficient sedative or analgesic agent that is considered by the examiner to confound the qualifying neurologic exam

2) Etiology of NE not likely to be hypoxic-ischemic in origin

3) Major congenital anomaly that may confound outcome

4) Considered to be moribund and will not be receiving full intensive care

- 5) Equipment and/or appropriate staff not available

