5.3 Baseline Patient Characteristics

Baseline characteristics will be compared across treatment groups. Table 1 in the MockTablesAppendix.docx document lists out maternal and neonatal characteristics that will be summarized in the primary published paper. In addition to the variables indicated in Table 1 of the MockTablesAppendix.docx document, other baseline characteristics may be investigated internally by the Premie Hypothermia Subcommittee. For programming purposes, the following list contains an example list of infant and maternal characteristics that will or may be investigated as well as dataset and variable names needed to locate the characteristics in the clinical database:

- Infant baseline characteristics (*Variable Type, Form, Variable name in clinical database*)
 - Birth year (*Multiple level discrete, PH05: A.1.a, PH5BRTDT*)
 - GA (*Multiple level discrete – at level of weeks, PH05: A.7.a, PH5GESTW*)
 - Sex (*Binary, PH05: A.8, PH5SEX*)
 - Birthweight (grams) (*Continuous, PH05: A.4, PH5BRTWT*)
 - Length (cm) (*Continuous, PH05: A.5, PH5BRTLN*)
 - Head circumference (cm) (*Continuous, PH05: A.6, PH5HCIRC*)
 - Seizures (*Binary, PH02: C.1, PH2SIEZ*)
 - Level of Encephalopathy (*Binary, PH02: G.4, PH2LECEP*)
 - Inborn/outborn status (*Binary, PH05: A.2, PH5OUTBN*)
 - 1-minute Apgar scores (*Continuous, PH05: A.3.a, PH5APG1*)

- 5-minute Apgar scores (*Continuous, PH05: A.3.b, PH5APG5*)
- Received resuscitation at delivery (*Binary, PH05: B.1-B.5, PH5OXYG / PH5BAGM / PH5CHCOM / PH5INTUB / PH5DRUGS. any equal to 'Y'*)
 - Types of resuscitation (*Multiple level discrete or individual binary, use PH05: B.1-B.5, PH5OXYG / PH5BAGM / PH5CHCOM / PH5INTUB / PH5DRUGS.*)
- Received resuscitation at 10 minutes (*Binary, PH05: C.1-C.5, PH5OXY10 / PH5BAG10 / PH5CHE10 / PH5INT10 / PH5DRG10. Any equal to 'Y'*)
 - Types of resuscitation (*Multiple level discrete or individual binary, use PH05: C.1-C.5, PH5OXY10 / PH5BAG10 / PH5CHE10 / PH5INT10 / PH5DRG10.*)

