- Received cord blood gas (*Binary, PH05: E.1, PH5CBGO, will be used in the construction of a derived variable containing cord blood gas information if non-missing and <1 hour of age information if cord blood gas information is missing and <1 hour of age information is non-missing. Stated another way: select cord gas if both cord gas and 1 hr gas are available and select 1 hr gas if cord not available. These variables are an intermediate step. See cord or postnatal variables below for variables that will actually get used in reports.*)
 - Source (*Multiple level discrete, PH05: E.1.a, PH5CBS*)
 - pH (*Continuous, PH05: E.1.b, PH5CBPH*)
 - PCO₂ (mmHg) (*Continuous, PH05: E.1.c, PH5CBPCO*)
 - PO₂ (mmHg) (*Continuous, PH05: E.1.d, PH5CBP02*)
 - HCO₃ (mEq) (*Continuous, PH05: E.1.e, PH5CBHCO*)
 - Base deficit (*Continuous, PH05: E.1.f, PH5CBBD*)
- Postnatal blood gas obtained at <1 hour of age (*Binary, PH05: E.2, PH5PNBGO, will be used in the construction of a derived variable containing cord blood gas information if non-missing and <1 hour of age information if cord blood gas information is missing and <1 hour of age information is non-missing. Stated another way: select cord gas if both cord gas and 1 hr gas are available and select 1 hr gas if cord not available. These variables are an intermediate step. See cord or postnatal variables below for variables that will actually get used in reports*)
 - Source (*Multiple level discrete, PH05: E.2.a, PH5PGS*)
 - pH (*Continuous, PH05: E.2.d, PH5PGPH*)
 - PCO₂ (mmHg) (*Continuous, PH05: E.2.e, PH5PGPCO*)
 - PO₂ (mmHg) (*Continuous, PH05: E.2.f, PH5PGPO2*)
 - HCO₃ (mEq) (*Continuous, PH05: E.2.g, PH5PGHCO*)
 - Base deficit (*Continuous, PH05: E.2.h, PH5PGBD*)
- Cord or postnatal (<1 hour of age) blood gas (*Combination of appropriate blood gas variables from the above two blood gas groups. Use Cord variable if non-missing and use <1 hour variable if cord variable is missing and <1 hour variable is non-missing. Stated another way: select cord gas if both cord gas and 1 hr gas are available and select 1 hr gas if cord not available. These variables will actually be the variables used in reports covering cord or postnatal blood gas.*)
 - pH (*Continuous*)
 - PCO₂ (mmHg) (*Continuous*)
 - PO₂ (mmHg) (*Continuous*)
 - HCO₃ (mEq) (*Continuous*)

- Base deficit (*Continuous*)
- Maternal baseline variables
 - Mother's age (*Continuous, PH04: A.1, PH4MAGE*)

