The prior for the random center effects will be Normal centered at 0, and the hyperprior for the standard deviation of the random center effect will be specified in Section 6.5.3. Any baseline covariates that are added to the model (in sensitivity analyses to adjust for important unbalanced baseline covariates) will either be coded using 0/1 indicator variables, sets of indicator variables, or as centered continuous covariates. Priors for these other to-be-determined covariates are specified in Section 6.5.3. Post processing will be used to get posterior approximations of relative risk and risk differences due to treatment. The logistic model will be fit to the data, then for each infant, the model parameter chains will be used to estimate the within subject posterior relative risk and risk difference which will equal hypothermia divided by normothermia and hypothermia minus normothermia respectively. A within subject estimate of relative risk will be calculated by setting

the treatment variable value to hypothermia, estimating the probability of outcome for all infants, repeating the same process after setting the treatment variable to normothermia then dividing the two probabilities of outcome for all infants, hypothermia over normothermia. A within subject estimate of risk difference will be calculated by setting the treatment variable value to hypothermia, estimating the probability of outcome for all infants, repeating the same process after setting the treatment variable to normothermia then subtracting the two probabilities of outcome for all infants, hypothermia minus normothermia. Since the parameter chains will contain at least 120,000 samples, each infant will contribute at least 120,000 samples for the approximation of the within subject relative risk posterior and the within subject risk difference posterior. Using all samples of relative risk and risk differences from all infants to approximate the posteriors, the mean estimate of relative risk and risk difference will be calculated as well as, 95% credible intervals of mean relative risk and risk difference. Finally, posterior probabilities of benefit due to hypothermia from both relative risk and risk differences will be used as summary statistics. Differences in the relative risk and risk difference posteriors will be reflected upon to better understand the estimated treatment effect.

For count outcomes like days or duration, y_{ij} , the main covariates will have the form:

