6.5.2 Covariates

All regression models will adjust for:

- level of encephalopathy at randomization and
- center (as a random effect).

The planned number of enrolling centers is 18, and center will be included in the linear component of the model as an additive random effect.

In addition to adjusting for level of encephalopathy and center as a random effect, sensitivity analyses will be completed by selecting baseline covariates that differ across the two treatments. These covariates will be selected from those covariates listed in section 5.3.

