6.5.3 Prior Specification (Binary/Ordinal Primary and Secondary Outcomes)

For the intercept and the encephalopathy terms, Normal(mean = 0, sd=1) priors will be used.

For any other covariates added to the model for sensitivity analyses or any exploratory model, a Normal(mean=0, sd=1) prior will be used.

For the random center effect, we will assume a Normal distribution centered at 0, and the standard deviation parameter will be assumed to follow a half-normal hyperprior with mean equal to 0 and standard deviation equal to 1.

For the term representing the log odds ratio of hypothermia treatment, skeptical, neutral, and enthusiastic priors will be used to estimate posterior distributions for odds ratio when analyzing the primary outcome and primary outcome components. For all other outcomes, only a neutral prior will be used. Because the logistic model will estimate the log odds ratio as the treatment parameter, the priors for the treatment effect will be normal priors on the log odds ratio scale. These normal priors for the log odds ratio are defined below so that the resulting priors in the odds ratio scale have specified properties.

On the odds ratio scale, the skeptical prior for odds ratio will be centered on 1.1 and have a 95% credible interval with an approximate range of 0.28 to 4.40. This skeptical prior will be defined by a normal prior on the log odds ratio scale centered at $\log(1.1) = 0.0953$ with standard deviation (SD) of 0.7072, Normal(mean = 0.0953, sd=0.7072).

On the odds ratio scale, the neutral prior for the odds ratio will be centered on 1.0 and have a 95% credible interval with an approximate range of 0.25 to 4.00. This neutral prior will be defined by a

normal prior on the log odds ratio scale centered at 0 with standard deviation (SD) of 0.7072, Normal(mean = 0, sd=0.7072). Similar priors will be used for the regressions involved in proportional odds modeling of secondary ordinal outcomes.

On the odds ratio scale, the enthusiastic prior for the odds ratio will be centered on 0.75 and have a 95% credible interval with an approximate range of 0.19 to 3.00. This enthusiastic prior will be defined by a normal prior on the log odds ratio scale centered at $\log(0.75) = -0.2877$ with standard deviation (SD) of 0.7072, Normal(mean = -0.2877, sd=0.7072).

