6.5.5 Final Analysis

The final analysis will occur after 168 infants have completed the trial, as specified earlier. The final analysis will not occur until all enrolled infants have a primary outcome determination, i.e. have the primary endpoint value assigned, classified as withdrawn without primary outcome assigned, or deemed lost to follow-up. Part of determining primary outcome of enrolled infants will involve masked adjudication of outcomes for infants who have an indeterminable outcome based on partially collected follow-up information. Once all enrolled infants have reached final status and primary endpoints determined, the clinical database will be exported, and study analysis datasets created. At that point, the analysis datasets will be considered “locked” and any further adjustments to the clinical datasets will not be included in the analysis datasets.

The final analysis will involve posterior distribution estimation for the effect of hypothermia relative to normal cooling. For binary outcomes, the effect will be the adjusted relative risk and adjusted risk differences calculated from a binomial regression model with logit link and post processing of

predicted outcome probabilities. For count outcomes, the effect will be the adjusted relative risk from the two groups obtained using negative binomial regression. For ordinal outcomes, the effect will be the adjusted odds ratio calculated from the cumulative logits.

For treatment relative risk estimation, posterior probabilities of >0%, >5%, >10% and >20% decrease in binary outcomes will be calculated. If θ is the relative risk defined as risk in cooling group over risk in control group, then the above specified posterior probabilities are, $\Pr(\theta < 1 | X)$, $\Pr(\theta < 0.95 | X)$, $\Pr(\theta < 0.9 | X)$, $\Pr(\theta < 0.8 | X)$. In addition to posterior probability calculations, graphical displays of the posterior distribution and appropriate 95% credible intervals for the over-all relative risk will be created. Finally, forest plots of the center level relative risks and 95% credible intervals will be created.

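### Added continuous covariates are centred but not scaled before a common Normal(0,1) prior, so an adjustment for blood pH would be partly shrunk away

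*SAP*

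**What the plan says.** Section 6.5.1 sets the coding of covariates added to the models in sensitivity analyses: they "will either be coded using 0/1 indicator variables, sets of indicator variables, or as centered continuous covariates". It says this for the binary, count and ordinal models alike, and mentions centring only.

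Section 6.5.3 sets the prior: "For any other covariates added to the model for sensitivity analyses or any exploratory model, a Normal(mean=0, sd=1) prior will be used". Section 6.5.4 repeats it for the count models. Section 4.1 describes the trial's priors in general as weakly informative.

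On which covariates may enter, section 6.5.2 says "These covariates will be selected from those covariates listed in section 5.3". That list holds continuous variables in very different units: birth weight in grams, PCO2 in mmHg, base deficit, and the pH of the derived variable "Cord or postnatal (<1 hour of age) blood gas".

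Sections 6.5.2 and 6.5.5 present the covariate-adjusted sensitivity analysis as planned. Section 6.5.7 leaves it to the subcommittee's discretion and limits it to the primary outcome and death. Section 6.5.5 also allows secondary analyses to be covariate-adjusted, in which case no unadjusted version is run.

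**The concern.** A prior on a regression coefficient has no fixed strength. It depends on the unit of the covariate. A Normal(0,1) prior on a log odds ratio per gram of birth weight constrains nothing. The same prior per whole unit of pH constrains a good deal, because infants in this trial will differ by only a fraction of a unit. The SAP's own intermediate acidemia band shows the scale: "cord or 1st hour of life blood gas with a pH of 7.01-7.15".

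Blood pH is an entry criterion and a natural candidate if the arms differ on it. A model reported as adjusted for pH would then be only partly adjusted, and its treatment estimate would be pulled toward the one without pH. A reader could take some of that agreement as evidence of robustness when it comes from the unit of measurement. Base deficit, from the same blood gas, would be almost fully adjusted.

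**Working it through.** **Inputs from the SAP.** N = 168 (section 6.5.5: "The final analysis will occur after 168 infants have completed the trial"). Event rate 60%, the average of the 70% and 50% in section 3.4, so p(1−p) = 0.24. Covariate prior Normal(0,1). Neutral treatment prior Normal(0, 0.7072).

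**Assumed, because the SAP gives no figure.** SD of pH 0.10 to 0.25. Outcome log odds of 0.6 per SD of pH.

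**1. Reproduce the stated prior interval.** exp(±1.96 × 0.7072) = 0.25 to 4.00, as section 6.5.3 states for the neutral treatment prior.

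**2. The same formula for the covariate prior.** No assumption is needed here.
- Per 0.1 pH: exp(±1.96 × 0.1) = 0.82 to 1.22.
- Over 0.15 pH, from 7.00 to 7.15: exp(±1.96 × 0.15) = 0.745 to 1.34.

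Both are far tighter than the treatment prior.

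**3. Share of the pH slope kept.** The data precision of the slope is about I = N × p(1−p) × SD² = 40.32 × SD². The prior precision is 1, so the share kept is I/(I+1).

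| SD of pH | I | Share kept |
|---|---|---|
| 0.10 | 0.40 | 29% |
| 0.15 | 0.91 | 48% |
| 0.20 | 1.61 | 62% |
| 0.25 | 2.52 | 72% |
| standardized (SD = 1) | 40.32 | 98% |

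Half the slope is lost when I = 1, that is at SD = √(1/40.32) ≈ 0.157.

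For death, the event rate is also an assumption. At 20% and SD 0.15, I = 168 × 0.16 × 0.0225 = 0.60, and 38% is kept.

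**4. Other candidates.** Under assumed SDs, the same formula keeps about 99% or more for base deficit, PCO2, birth weight, maternal age, head circumference and Apgar score. Among the covariates checked, only pH is affected.

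**5. What a plausible imbalance is.** With 84 per arm, the standard error of the difference in means is √(2/84) = 0.154 SD. An imbalance of 0.3 SD is 0.3/0.154 ≈ 1.9 standard errors, about p = 0.05. An imbalance of 0.5 SD is about 3.2 standard errors, roughly a 0.1% event under randomization.

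**6. Effect on the treatment estimate at 0.3 SD.** The full pH contribution is 0.3 × 0.6 = 0.18 on the log odds scale. The treatment coefficient has data precision of about 168 × 0.24/4 = 10.08 and prior precision 1/0.7072² = 2.0. It is therefore shrunk by 10.08/12.08 = 0.83, with posterior SD 1/√12.08 = 0.29. The gap between the raw-unit and the standardized adjustment is about 0.18 × (0.976 − share kept) × 0.83:
- SD 0.10: 0.10
- SD 0.15: 0.07
- SD 0.20: 0.05
- SD 0.25: 0.04

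Simulated posterior-mode fits gave 0.10, 0.07, 0.06 and 0.04. Against the posterior SD this is 0.04/0.29 ≈ 0.14 to 0.10/0.29 ≈ 0.34.

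**7. Simulation check at the extreme imbalance.** 800 data sets per setting were fitted by posterior mode, with 0.5 SD imbalance, no true treatment effect, odds ratios of 1.5 to 2.5 per SD of pH, and the center effect omitted. Relative to a near-flat prior, the raw-unit prior removed 27–28%, 45–46%, 57–60% and 67–70% of the pH-related bias at SDs of 0.10, 0.15, 0.20 and 0.25. Scaled pH removed 97% throughout. At SD 0.15 and odds ratio 2 per SD, the bias in the treatment log odds ratio was 0.256 unadjusted, 0.138 under the SAP's prior and 0.005 with scaled pH.

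**The case against.** The strongest case against is that this may never arise, and would be modest if it did.
- pH enters only if the arms differ on it and the subcommittee chooses to adjust.
- Section 6.5.1 also permits indicator coding. A 0/1 split of pH would comply, and a Normal(0,1) prior on a 0/1 term is what the plan already uses for encephalopathy.
- Base deficit is available as a companion measure and is unaffected.
- The primary model adjusts only for encephalopathy and center.
- At an imbalance that randomization would plausibly produce, the estimate moves by at most about a third of a posterior SD.

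All of this stands, and it limits the weight of the point. It does not remove it. Continuous coding is equally permitted, section 5.3 lists pH as continuous, and no text says that it is rescaled. An analyst following the plan literally gets the partial adjustment. Where a secondary analysis is covariate-adjusted, section 6.5.5 rules out an unadjusted version that might reveal it.

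A reader might go further and infer that pH adjustment is largely shrunk away, that the confounding stays in place, or that continuous covariates in general are mishandled. The SAP does not support this. More than half the slope is lost only if the SD of pH is below about 0.157, and the SAP gives no SD. At 0.20 to 0.25 most of the adjustment survives. The 0.5 SD example illustrates the mechanism but is not a likely case.

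**Conclusion.** The gap in the specification is real and minor. As written, the covariate prior is close to flat for most candidates but informative for blood pH, which sits poorly with the weakly informative intent of section 4.1.

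The consequence is confined to the sensitivity analyses of the primary outcome and death and to any covariate-adjusted secondary analyses, and only if pH is unbalanced and entered as continuous. There the adjustment is incomplete by an amount that depends on the SD of pH. The prior interval per 0.1 pH is exact. Confidence in the size of the effect is moderate, because it rests on the assumed SD, the assumed strength of pH as a predictor and the 60% event rate.

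**What to change.** In section 6.5.1, in each place where the coding of added covariates is described, state that continuous covariates are centred and divided by their sample SD before the Normal(0,1) prior of section 6.5.3 or 6.5.4 is applied. In the simulations this kept 98–101% of the true pH slope. At a minimum, state that pH is entered per 0.1 unit. An SD of 0.10 then becomes 1.0 on the new scale and about 98% of the slope is kept, with more at larger SDs.

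The cost is a sentence in the SAP and a line of code. The primary model does not change.

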- Posterior plot of treatment effect
- Posterior median and posterior standard deviation
- 95% credible interval
- For relative risk, posterior probabilities of >0%, >5%, >10%, and >20% decrease in the primary outcome will be calculated
- For risk difference, posterior probabilities of >0%, >1%, >2%, >3%, and >5% decrease in primary outcome will be calculated
- forest plot of the center level effect and 95% credible intervals.

If the FAS analysis of the primary outcome results in any clinically notable findings, then the primary outcome may also be analyzed in an exploratory fashion using the PP population.

Analysis of Secondary Outcomes

With respect to secondary outcomes, analyses will follow the same process as the primary outcome analysis defined above. See MockTablesAppendix.docx for list of selected variables.

Analysis of Safety (AE) and Hospital Outcomes

Safety and hospital outcomes listed in Sections 6.2 and 6.3 will be analyzed using the FAS population and if necessary, the PP population using relative risk models, proportional odds models, or Negative Binomial models, depending on the type of outcome.

With respect to binary safety outcomes, the estimated posterior distribution of relative risk, θ , based on the data and the neutral prior will be used to determine posterior probabilities of harm from the intervention, $\Pr(\theta > 1 | X)$, as well as 95% credible intervals.

For ordinal safety outcomes, the estimated posterior distribution odds ratio for the cumulative logits, ϕ , will be estimated based on the data and the neutral prior. In addition, posterior probabilities of harm, $\Pr(\phi > 1 | X)$, and 95% credible intervals of ϕ will be calculated.

For count type safety outcome, the estimated posterior distribution of the treatment mean rate, ϕ , will be estimated based on the data and the neutral prior. In addition, posterior probabilities of harm, $\Pr(\phi > 1 | X)$, and 95% credible intervals of ϕ will be calculated.

Analysis of Ultrasound, CT scan, MRI and encephalopathy outcomes

Ultrasound, CT scan, MRI, and encephalopathy outcomes will be analyzed using the FAS population. Head ultrasounds, CT scans, and brain MRIs will be summarized by treatment and time (prior to intervention, during intervention, after intervention, any time). Summaries will be created for number of babies with any abnormal findings during time period data recorded, and for total events across all babies during any time period.

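### SAP 6.5.1 averages each infant's own risk ratio, which is not the ratio of group risks that 6.5.5 defines as the primary relative risk

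*SAP*

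**What the plan says.** SAP 6.5.1 fits a logistic model with a random center intercept, an encephalopathy term and a treatment term. Each infant's outcome probability is then predicted under hypothermia and under normothermia, and the relative risk comes from "dividing the two probabilities of outcome for all infants, hypothermia over normothermia". Read alone, that phrase could mean one ratio of totals. The text around it rules this out: the ratio is called within-subject, and "each infant will contribute at least 120,000 samples for the approximation of the within subject relative risk posterior". The infants are then combined: "Using all samples of relative risk and risk differences from all infants to approximate the posteriors", after which "the mean estimate of relative risk and risk difference will be calculated", with 95% credible intervals and probabilities of benefit.

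SAP 6.5.5 defines theta as "relative risk defined as risk in cooling group over risk in control group". For that theta, "posterior probabilities of >0%, >5%, >10% and >20% decrease in binary outcomes will be calculated", that is, Pr(theta<1), Pr(theta<0.95), Pr(theta<0.9) and Pr(theta<0.8). The output list for the primary outcome in 6.5.5 names "Posterior median and posterior standard deviation", whereas 4.1 and 6.5.1 name the mean.

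**The concern.** The two sections describe different quantities under one name. A ratio of group risks weights each infant's ratio by that infant's baseline risk. The 6.5.1 average weights all infants equally.

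SAP 4.1 shows how the gap could open. It says the protocol specified a log-binomial model, in which one relative risk applies to every infant and the two definitions coincide. The change to logistic regression with post-processing ended that equality, and 6.5.5 still states the group definition.

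At stake is the reported primary RR under all three priors, with its interval and graded probabilities. The mean risk difference is not affected, because averaging is linear. SAP 6.5.1 plans to reflect on differences between the RR and RD posteriors, so an averaging artefact could be taken for a finding.

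**Working it through.** **1. The plan's own figure.** Three chains of 200,000 samples thinned by 5 give 3 × 200,000 / 5 = 120,000 draws, as stated. Each infant contributes that many ratios, so with 168 infants the pool holds 168 × 120,000 = 20,160,000 values. This confirms one ratio per infant per draw.

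**2. Algebra.** Let p0 be an infant's risk under normothermia and OR the common odds ratio.
- Infant ratio: RR_i = OR / (1 − p0_i + OR × p0_i). It is nearer 1 where p0_i is high.
- 6.5.5 quantity: sum(p1_i) / sum(p0_i) = sum(p0_i × RR_i) / sum(p0_i).
- 6.5.1 mean: average of RR_i.
- Group ratio minus mean of ratios = Cov(p0, RR_i) / mean(p0). This is positive for OR<1, zero for OR=1 and negative for OR>1.

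**3. Fixed-parameter example.** The 70% control risk is the planning figure in SAP 3.4. The split is assumed: 60% risk in moderate and 93.3% in severe encephalopathy, 30% severe.
- OR 0.5: moderate 0.60 to 0.4286 (RR 0.714); severe 0.933 to 0.875 (RR 0.937). Mean of ratios 0.7 × 0.714 + 0.3 × 0.937 = 0.781. Group ratio 0.5625 / 0.70 = 0.803.
- OR 2: moderate 0.60 to 0.75 (RR 1.250); severe 0.933 to 0.9655 (RR 1.034). Mean of ratios 1.185. Group ratio 0.8147 / 0.70 = 1.164. Harm is inflated too.
- OR 0.5 with closer strata (65% and about 82%): 0.772 against 0.777.
- Risk difference at OR 0.5: 0.7 × (−0.1714) + 0.3 × (−0.0583) = −0.1375 = 0.5625 − 0.70. Both routes agree.

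**4. Posterior under the SAP model.** Neutral prior, 168 infants, 18 centers, 150 simulated trials per scenario. Severity risks, severe share and center SD (0.5) are assumptions. Scenario A: risks 62%/90%, 25% severe. Scenario B: 55%/95%, 35% severe. Scenario C: as A, but with encephalopathy coded as printed in 6.5.1 (mild against moderate or severe, hence constant among eligible infants). Each cell gives group ratio / SAP pooled.

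| Scenario, true RR | Mean | Median | Pr(<1) | Pr(<0.95) | Pr(<0.9) | Pr(<0.8) | Interval width |
|---|---|---|---|---|---|---|---|
| A, 0.70 | 0.756 / 0.736 | 0.753 / 0.737 | 0.977 / 0.977 | 0.948 / 0.925 | 0.893 / 0.837 | 0.663 / 0.628 | 0.338 / 0.499 |
| A, 0.80 | 0.865 / 0.853 | 0.862 / 0.860 | 0.867 / 0.867 | 0.767 / 0.727 | 0.627 / 0.581 | 0.301 / 0.341 | 0.356 / 0.484 |
| A, 1.00 | 1.007 / 1.011 | 1.003 / 1.003 | 0.499 / 0.499 | 0.331 / 0.307 | 0.183 / 0.188 | 0.031 / 0.062 | 0.355 / 0.491 |
| A, 1.10 | 1.099 / 1.118 | 1.094 / 1.088 | 0.211 / 0.211 | 0.104 / 0.099 | 0.042 / 0.050 | 0.003 / 0.011 | 0.364 / 0.576 |
| B, 0.80 | 0.843 / 0.817 | 0.840 / 0.831 | 0.914 / 0.914 | 0.834 / 0.750 | 0.711 / 0.607 | 0.361 / 0.419 | 0.329 / 0.535 |
| C, 0.80 | 0.851 / 0.846 | 0.847 / 0.848 | 0.889 / 0.889 | 0.804 / 0.795 | 0.682 / 0.664 | 0.353 / 0.360 | 0.364 / 0.431 |

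Pr(<1) is identical because, within a draw, every infant's ratio lies on the same side of 1. The interval widens because pooling adds between-infant spread, which also pulls Pr(<0.95) and Pr(<0.9) down when there is benefit.

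Fits of the example in step 3 (center SD 0.5, 30 simulated trials per OR) agree. The mean is 0.865 / 0.848 at OR 0.5 and 0.797 / 0.774 at OR 0.41. Pr(<0.8) is 0.29 / 0.35 and 0.53 / 0.52.

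**5. Is this only the pooling problem?** No. In A at true RR 0.70, averaging infant ratios within each draw, without pooling, still gives a mean of 0.736 against 0.756. Pr(<0.9) is then 0.908 against 0.893 and Pr(<0.8) 0.717 against 0.663.

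**The case against.** **The construction is disclosed.** SAP 6.5.1 openly calls the ratio within-subject, and 4.1 cites a paper on average predictive comparisons. The clause in 6.5.5 could be read as fixing only which arm is the numerator. The disclosure stands, and the cited paper is not at hand, so nothing is claimed about departure from it. But 6.5.5 does more than set direction: it names the group risks as the two parts of the ratio and attaches the threshold probabilities to that ratio. Nothing in the SAP links it to an equally weighted average of infant ratios.

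**The effect is small and depends on assumed contrasts.** This stands. The SAP gives no risks by severity. Closer strata or the printed encephalopathy coding leave a shift in the mean of about 0.005.

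**A stronger reading.** A reader might infer that the construction exaggerates benefit and inflates all the graded probabilities. The SAP's procedure does not support that. The mean moves away from 1 in both directions. Pr(RR<1), the criterion in the design statement of SAP 3.4, is untouched. With the pooling that 6.5.1 prescribes, Pr(<0.95) and Pr(<0.9) fall in every benefit scenario run, and Pr(<0.8) goes either way. Uniform gains at the thresholds appear only if infant ratios are averaged within each draw, which the SAP does not say. Nor can it be said that the RR would clash with tabulated adjusted group risks, since 6.5.5 does not list them as outputs.

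**Conclusion.** SAP 6.5.1 and 6.5.5 define the primary RR differently, and under the SAP's logistic model the difference is real whenever the odds ratio is not 1 and baseline risks vary. The direction of the shift in the mean follows from algebra; its size rests on assumed severity risks, severe share and center spread. In the fitted benefit and harm scenarios the posterior mean lies about 0.005 to 0.03 further from 1. The median moves by at most 0.016 in the scenarios shown, and not always away from 1. The graded probabilities are misstated relative to the 6.5.5 theta, not uniformly overstated. Pr(RR<1) and the mean risk difference are unaffected. The effect is modest, but it concerns the primary treatment effect and is nearly free to correct, so it should be corrected.

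**What to change.** In SAP 6.5.1, replace the within-subject ratio. For each posterior draw, average the predicted risks over all infants with treatment set to hypothermia, and again with treatment set to normothermia. Take RR as the first mean divided by the second, and RD as the first minus the second. Base the point estimate, credible interval, posterior plot and all threshold probabilities on these per-draw values, and name one point summary in 4.1, 6.5.1 and 6.5.5.

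The cost is a few sentences and about one line of post-processing code. The mean RR moves slightly toward 1; in the benefit scenarios run, Pr(<0.95) and Pr(<0.9) rise and the interval narrows. The same edit removes the separate problem of pooling infant-level draws, so the two points should be presented together.
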